Attachment 2. Clinical Laboratory Tests

Clinical Laboratory Tests

Hematology^a:		Clinical Chemistry^a:
Hemoglobin		Sodium
Erythrocytes		Potassium
Platelets		Total bilirubin
Leukocytes (WBC)		Alkaline phosphatase
Neutrophils, segmented + bands		Alanine aminotransferase / serum glutamic pyruvic transaminase (ALT/SGPT)
Eosinophils		Aspartate aminotransferase / serum glutamic oxaloacetic transaminase (AST/SGOT)
Monocytes		Blood urea nitrogen (BUN)
Basophils		Creatinine
Lymphocytes:		Uric acid
• Total T- and B-cell counts		Calcium
• CD8 T cell counts		Glucose, random
• CD4 T cell counts		Albumin
• T regulatory counts (eg, CD4 ⁺ CD25 ⁺ FoxP3 ⁺)		Total protein
		Phosphorus
FoxP3^a		S100 β
		LDH
Troponin I^b		Cystatin C
		TGF β
Serum Pregnancy Test (females only)^{a,b}		PF4
BNP^a		ECG Chemistry^a:
		Lipase
High-sensitivity C-reactive protein (hs-CRP)^a		Thyroid Stimulating Hormone (TSH)
		Tri-iodothyronine (T3)
Urinalysis^b:		Thyroxine (T4)
pH		Albumin ^c
Protein		Glucose, random (non-fasting) ^c
Specific gravity		Calcium ^c
Glucose		Sodium ^c
Ketones		Potassium ^c
Blood		Phosphorus ^c
Leukocyte esterase		Magnesium ^c

Abbreviations: BNP = brain natriuretic peptide; ECG = electrocardiogram; LDH = lactate dehydrogenase; PF4 = platelet factor 4; TGF β = transforming growth factor-beta; WBC = white blood cells.

- a All samples will be discarded within 60 days of validated test results. Validation will either occur immediately after initial testing, or will require that samples be held to be retested at some defined time point. Laboratory tests will be analyzed by a central laboratory selected by Lilly.
- b All samples will be discarded within 60 days of validated test results. Validation will either occur immediately after initial testing, or will require that samples be held to be retested at some defined time point. Patients may be enrolled on local laboratory values only.
- c Test not performed if both chemistry and ECG chemistry required at same time point. See [Attachment 1](#).

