5.6.4.2. Part B of Study H9H-MC-JBAH – Combination of LY2157299 Monohydrate with Lomustine

After establishing the safety of LY2157299 monohydrate as a monotherapy up to the exposure considered to be safe, 2 cohorts with each [CC1]-mg/day and [CC1]-mg/day dose were evaluated in combination with lomustine. In Study JBAH Part B, no distinction was made between relatedness of AEs to either LY2157299 monohydrate or lomustine, where the study therapy was LY2157299 monohydrate in combination with lomustine.

As of 19 August 2011, the most common TEAE related to study therapy was thrombocytopenia (CC1 of [CC1] patients dosed [CC1%]). Other hematologic TEAEs related to study therapy included neutropenia, lymphopenia, and leucopenia affecting [] to [] patients (CC1 []% to []%). These are in line with the observed toxicity profile for lomustine. Other reported study therapy related TEAEs were fatigue, nausea, and dysgeusia, affecting [] or [] patients dosed ([]% to []%). Of the TEAEs that were not considered related to study therapy, 1 patient had an isolated prolonged Common Terminology Criteria for Adverse Events (CTCAE) Grade 3 QTc interval and was not considered serious because of its isolated observation.

Based on these observations the proposed dose for Phase 2 development is [CC1] mg/day given as a 14-days-on/14-days-off cycle.

More information about the known and expected benefits, risks and reasonably anticipated AEs may be found in the IB. Information on AEs expected to be related to the study drug may be found in Section 7 (Development Core Safety Information [DCSI]) of the IB. Information on serious adverse events (SAEs) expected in the study population independent of drug exposure and that will be assessed by the sponsor in aggregate periodically during the course of the study may be found in Section 6 (Effects in Humans) of the IB.

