8.1.2. Postdiscontinuation Follow-Up Period Assessments

Terms used to describe the postdiscontinuation of study treatment are defined below:

- **Postdiscontinuation Follow-Up:** Begins the day after the patient and the investigator agree that the patient will no longer continue study treatment.
 - **The short-term follow-up period** begins 1 day after discontinuation of study treatment and lasts approximately 30 days (Visit 801).
 - **The long-term follow-up period** begins 1 day after the short-term follow-up period (Visit 801) is completed and continues until death or study completion to collect survival data.

The Study Schedule ([Attachment 1](#)) describes all assessments for the post discontinuation and follow up periods. All patients should be followed and all AEs (Section [10.3](#)) reported for a minimum of 30 days from the date of discontinuation or until completion of Visit 801.

At Visit 801, physical examinations, ECOG PS evaluation, health outcome assessments (Section [10.2](#)), ECG/ECG chemistry (Section [10.3.2.1](#)), ECHO/Doppler (Section [10.3.2.2](#)), serum chemistry, urinalysis, and hematology laboratory tests (Section [10.4.1](#)) will be completed. Additionally, after Visit 801, ECG/ECG chemistry and ECHO/Doppler will be performed as indicated in Section [10.3.2.1](#) and Section [10.3.2.2](#), respectively.

After discontinuation, tumor measurements will be performed as indicated in Section [10.1.2](#).

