Attachment 1. JBAL Study Schedule

Study Schedule for Protocol H9H-MC-JBAL – Prestudy and Cycle 1

Cycle	Prestudy			Cycle 1								Comments
	Relative Day	≤28	≤14	≤7	1	3	7±2	12±2	14	15	16	26±2
Treatment												
Lomustine						X						
LY2157299 monohydrate or matched placebo				X	X	X	X	X				CCI
Procedures												
Informed consent	X											
Medical history		X										
Pregnancy test		X										CCI
Physical Examination		X		X								
Vital signs (heart rate, blood pressure)		X		X								
CTCAE		X		X								
Concomitant medications		X		X								

Cycle	Prestudy			Cycle 1							Comments	
	Relative Day	≤ 28	≤ 14	≤ 7	1	3	7 ± 2	12 ± 2	14	15	16	
Relative Day	≤ 28				1	3	7 ± 2	12 ± 2	14	15	16	26 ± 2
Within a Cycle												
ECOG performance status		X		X								
Health outcome measures		X									X	
Imaging Procedures												
Echocardiography with Doppler		X										
Radiological tumor assessment		X										
Chest CT scan or chest MRI		X										
Laboratory/Diagnostic Tests												
PFT			X									
ECG		X		X	X			X	X		X	
Troponin I and BNP			X								X	
Hematology			X								X	
Urinalysis			X								X	
Fox P3			X									

CCI

Cycle	Prestudy			Cycle 1							Comments	
	Relative Day	≤ 28	≤ 14	≤ 7	1	3	7 ± 2	12 ± 2	14	15	16	
Relative Day	≤ 28	≤ 14	≤ 7		1	3	7 ± 2	12 ± 2	14	15	16	26 ± 2
Serum chemistry			X								X	
ECG chemistry		X		X	X			X	X			
Serum hs-CRP			X									X
PK sampling				X	X			X	X	X		
CSF												
MAP				X			X					
Affymetrix				X								
Whole blood for PGx		X										
Whole blood/plasma				X								
Tumor tissue		X										

Study Schedule for Protocol H9H-MC-JBAL – Cycles 2, 5, 8, 11

Cycle	Cycles 2, 5, 8, 11					Comments
Relative Day Within a Cycle	1±2	6±2	12±2	21±2	26±2	
Treatment						
Lomustine				X		
LY2157299 monohydrate or matched placebo	X	X	X			
Procedures						
Physical examination	X		X			
Vital signs (heart rate, blood pressure)	X					
CTCAE	X					
Concomitant medications	X					
ECOG performance status	X					
Health outcome measures					X	
Echocardiography with Doppler					X	
ECG					X	
Tropionin I and BNP					X	
Hematology					X	
Urinalysis					X	
Fox P3					X	
Serum chemistry					X	

CCI

ECG chemistry					X	
Cycle	Cycles 2, 5, 8, 11					Comments
Relative Day Within a Cycle	1±2	6±2	12±2	21±2	26±2	
Serum hs-CRP					X	
Radiological tumor assessment					X	CCI
MAP			X			
Affymetrix					X	

Study Schedule for Protocol H9H-MC-JBAL – Cycles 3, 6, 9, 12

Cycle	Cycles 3, 6, 9, 12				Comments

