Relative Day Within a Cycle	1±2	6±2	12±2	26±2	
Treatment					
Lomustine					
LY2157299 monohydrate or matched placebo	X	X	X		
Procedures					
Physical examination	X				
Vital signs (heart rate, blood pressure)	X				
CTCAE	X				
Concomitant medications	X				
ECOG performance status	X				
Health outcome measures				X	
Echocardiography with Doppler				X	
ECG				X	
PFT				X	
Troponin I and BNP				X	
Hematology				X	
Fox P3				X	

CCI

Cycle	Cycles 3, 6, 9, 12				Comments
Relative Day Within a Cycle	1±2	6±2	12±2	26±2	
Serum chemistry				X	
ECG chemistry				X	
Serum hs-CRP				X	
Radiological tumor assessment				X	
Chest CT scan or chest MRI				X	
MAP				X	
Affymetrix				X	

CCI

Study Schedule for Protocol H9H-MC-JBAL – Cycles 4, 7, 10, Visit 801, Follow-Up

Cycle	Cycles 4, 7, 10				Visit 801	Follow Up	Comments
Relative Day Within a Cycle	1±2	6±2	12±2	26±2			
Treatment							
Lomustine		X					
LY2157299 monohydrate or matched placebo	X	X	X				
Procedures							
Physical examination	X				X		
Vital signs (heart rate, blood pressure)	X				X		
CTCAE	X				X		
Concomitant medications	X				X		
ECOG performance status	X				X		
Health outcome measures				X	X		
Echocardiography with Doppler				X	X	X	
ECG				X	X	X	
Troponin I and BNP				X	X		

Hematology				X	X	CC1	
Cycle	Cycles 4, 7, 10				Visit 801	Follow Up	Comments
Relative Day Within a Cycle	1±2	6±2	12±2	26±2			
Urinalysis				X	X		
Serum chemistry				X	X		
ECG chemistry				X	X	X	
Fox P3				X			
Serum hs-CRP				X			
Radiological tumor assessment				X			
MAP				X			
Affymetrix				X			

Abbreviations: BNP = brain natriuretic peptide; COWA = Controlled Oral Word Association; CSF = cerebrospinal fluid; CT = computed tomography; CTCAE = Common Terminology Criteria for Adverse Events; ECG = electrocardiogram; ECOG = Eastern Cooperative Oncology Group; GB = glioblastoma; hs-CRP = high-sensitivity C-reactive protein; HVLT-R = Hopkins Verbal Learning Test – Revised; MAP = multi-analyte panel; MDASI-BT = MD Anderson Symptom Inventory-Brain Tumor; MRI = magnetic resonance imaging; PFT = pulmonary function test; PGx = pharmacogenetics; PK = pharmacokinetic; TGF-β = transforming growth factor – beta.

Study Schedule for the continued access period only, Protocol H9H-MC-JBAL

Cycle	Continued Access ^a Visit 501-5XX				Follow-Up ^b Visit 801	Comments
	1±2	6±2	12±2	26±2		
Relative Day Within a Cycle						
Treatment						
Lomustine		X				
LY2157299	X	X	X			
Procedures						
Physical examination	X				X	

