6.13.6. Electrocardiograms

Electrocardiogram (ECG) assessment of normality and clinical significance will be listed by treatment group. Myocardial information and quantitative results including PR, QRS, QTcB (Bazett's correction), QTcF (Fridericia's correction) and RR intervals will be provided in patient listings. In addition, listings and summaries of outlying corrected QT intervals (QTc, QTcB and QTcF) will be provided for each scheduled time point.

Baseline ECGs are ECGs performed either during screening or predose during the study. Changes in QT from baseline, delta QT, will be calculated by subtracting the respective reading taken at the same nominal time during screening from the reading taken after LY2157299 dosing on specified days as per protocol schedule. Similarly, changes in RR from baseline (ie. delta RR) will be calculated. Delta QT will then be analyzed using a linear mixed-effects model with treatment arm, timepoint and delta RR as fixed effects, treatment-by-time interaction and patient as a random effect (Dmitrienko and Smith 2003). Least square means by timepoint and treatment arm together with 90% confidence intervals will be provided. Mean differences and 90% confidence intervals between treatment arms will be estimated from the model.

If data warrant, additional exploratory analyses may be conducted using appropriate modeling techniques.

The ECG chemistry laboratory values will be listed and summarized separately from other laboratory values.

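### As written, footnote c in Protocol Attachment 2 leaves magnesium unmeasured at all 12 scheduled ECG time points from Cycle 2 to Visit 801 of the main study schedule

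*Protocol*

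**What the plan says.** Protocol Attachment 2 lists a Clinical Chemistry panel and a separate ECG Chemistry panel. Seven ECG Chemistry analytes carry footnote c: albumin, glucose, calcium, sodium, potassium, phosphorus and magnesium. The footnote reads "Test not performed if both chemistry and ECG chemistry required at same time point" and refers the reader to Attachment 1.

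Attachment 1 gives the timing. In the table headed "Study Schedule for Protocol H9H-MC-JBAL – Cycles 2, 5, 8, 11", the ECG, serum chemistry and ECG chemistry are all marked on Day 26±2. The tables for Cycles 3, 6, 9, 12 and for Cycles 4, 7, 10 do the same. The last of these also covers Visit 801 and Follow Up. Its serum chemistry row reads "Serum chemistry X X" (Day 26±2 and Visit 801), and its ECG chemistry row reads "ECG chemistry X X X" (the same two, plus Follow Up). Protocol Section 8.1.2 lists ECG and ECG chemistry for Visit 801 and, in the same sentence, "ECHO/Doppler (Section [10.3.2.2](#)), serum chemistry, urinalysis, and hematology laboratory tests (Section [10.4.1](#)) will be completed".

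SAP Section 6.13.6 says that "listings and summaries of outlying corrected QT intervals (QTc, QTcB and QTcF) will be provided for each scheduled time point". It also plans a mixed model for delta QT, and lists and summarizes ECG chemistry separately from the other laboratory values.

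**The concern.** A rule against running an analyte twice is sensible when the analyte is in both panels. Magnesium is in only one, so the rule deletes the test instead of de-duplicating it.

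The pattern looks unintended. The sponsor put magnesium in a panel named for the ECG, and it is due wherever that panel stands alone. Continued access, which Protocol Section 5.7.1 describes as having fewer visits and tests, therefore keeps magnesium, while the fuller treatment schedule loses it from Cycle 2 on. No reason is given.

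At stake is the completeness of the electrolyte data that accompany the ECGs from Cycle 2 onward, including those that enter the planned QTc outlier listings.

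**Working it through.** The plan states no figure to reproduce. The check compares two lists and then counts visits.

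**Step 1: the two panels (Protocol Attachment 2).**

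| Analyte with footnote c | Also in Clinical Chemistry? |
|---|---|
| Albumin | yes |
| Glucose | yes |
| Calcium | yes |
| Sodium | yes |
| Potassium | yes |
| Phosphorus | yes |
| Magnesium | no |

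So 7 − 6 = 1 analyte, magnesium, has no counterpart. It appears nowhere else in Attachment 2.

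**Step 2: the visits (Protocol Attachments 1 and 3).** Under footnote c, magnesium is due only where ECG chemistry is marked and serum chemistry is not.

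| Time point | ECG | Serum chemistry | ECG chemistry | Magnesium due |
|---|---|---|---|---|
| Screening, ≤14 days | yes | no (marked at ≤7 days) | yes | yes |
| Cycle 1 Days 1, 3, 14, 15 | yes | no | yes | yes |
| Cycle 1 Day 26±2 | yes | yes | no | no |
| Day 26±2, Cycles 2, 5, 8, 11 | yes | yes | yes | no |
| Day 26±2, Cycles 3, 6, 9, 12 | yes | yes | yes | no |
| Day 26±2, Cycles 4, 7, 10 | yes | yes | yes | no |
| Visit 801 | yes | yes | yes | no |
| Follow Up after Visit 801 | yes | no | yes | yes |
| Continued access, including its own Visit 801 | yes | no | yes | yes |

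Scheduled ECG time points from Cycle 2 to Visit 801 in the main schedule: 4 + 4 + 3 = 11 cycles, plus Visit 801, gives 12. Both panels coincide at 12 of 12, so magnesium is due at 0 of 12. With the fix below it would be due at 12 of 12.

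Cycle 1 Day 26±2 also lacks magnesium, but because ECG chemistry is not scheduled there. Footnote c plays no part, and that visit is not in the count.

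**Step 3: where these visits fall relative to dosing.** LY2157299 is given on Days 1 to 14 of each cycle (Protocol Section 9.1). Day 26±2 is Day 24 to Day 28, so the ECG comes 24 − 14 = 10 to 28 − 14 = 14 days after the last scheduled dose. Visit 801 comes about 30 days after discontinuation (Protocol Section 8.1.2).

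**The case against.** Several points limit the concern, and most of them stand.

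- **Redaction.** Footnote c points to Attachment 1, whose Comments column is blacked out in the main schedules. A hidden instruction could restore magnesium. This cannot be excluded, but no visible text does so.
- **QTc attribution.** A reader might infer that QTc outliers from Cycle 2 on can no longer be separated into drug effect and low magnesium. The documents do not support that. The in-cycle ECGs fall 10 to 14 days after the last scheduled dose of a drug that Protocol Section 5.6.5.2 describes as having a relatively short half-life. The dosing-linked ECGs in Cycle 1 do have magnesium. Potassium, calcium and sodium are still measured at the shared visits through Clinical Chemistry. Nothing visible bars an unscheduled magnesium test.
- **Prior QTc case.** Protocol Section 5.6.4.2 reports that "1 patient had an isolated prolonged Common Terminology Criteria for Adverse Events (CTCAE) Grade 3 QTc interval". The same sentence places it among events not considered related to study therapy and says that it was not considered serious. It is weak support for a QT signal.
- **Between-arm bias.** A reader might infer that vomiting on lomustine would make magnesium differ between the lomustine arms and the monotherapy arm. This is speculative. Protocol Section 9.4 places nausea and vomiting about 6 hours after intake. By the nominal days, Day 26 is 26 − 21 = 5 days after lomustine in Cycles 2, 5, 8, 11, and 26 − 6 = 20 days after it in Cycles 4, 7, 10. Cycles 3, 6, 9, 12 have no lomustine mark. Both arms of the primary comparison receive lomustine.
- **Use in analysis.** The delta-QT model in SAP Section 6.13.6 contains arm, time point, delta RR, the arm-by-time interaction and patient. No planned model uses magnesium.
- **Twelve is a ceiling.** Median PFS on lomustine in Protocol Table JBAL.5.1 is 1.64 months and 82 days. At an assumed 30.4 days per month this is 1.64 × 30.4 / 28 = 1.8 cycles and 82 / 28 = 2.9 cycles. Many patients would reach only a few of these visits.

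None of this removes the mismatch between the footnote and the two lists.

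**Conclusion.** The point holds as a wrong rule in the laboratory schedule. Followed as written, footnote c yields magnesium at 0 of 12 scheduled ECG time points from Cycle 2 to Visit 801, where its evident purpose was only to avoid duplicates. The conclusion is confined to the main study schedule and rests on the visible marks in Attachment 1, with the redacted comments unseen.

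The consequence is modest: one electrolyte of the sponsor's own ECG panel is missing when ECG findings at visits mostly off LY2157299 are reviewed. Overall survival, sample size, the primary analysis and the delta-QT model are untouched. The documents do not support going further, to uninterpretable QTc outliers or to bias between arms. The case for correcting it is that the error is clear and very cheap to remove.

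**What to change.** Reconcile footnote c with the two lists in Protocol Attachment 2. Either remove it from magnesium or add magnesium to Clinical Chemistry, and keep it for the six analytes in both lists. If the redacted Attachment 1 comments already provide for magnesium, say so in the footnote.

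The cost is one footnote letter or one added analyte, a central-laboratory panel setting, and one assay on blood already drawn.

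Optionally, SAP Section 6.13.6 could state that the six shared analytes are taken from the chemistry panel at shared visits. Read literally, the separate ECG chemistry summary would otherwise hold only lipase, TSH, T3 and T4 there. This is a matter of presentation, since the six are already listed under chemistry (SAP Section 6.13.4).

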Attachment 3. Pharmacokinetic Sampling

In conjunction with the Study Schedule of Events, the following PK draws will be conducted.

Sparse PK Sampling Schedule for Phase 2

Sample Number	Cycle	Day	Sampling Windows for plasma PK	ECG and ECG Chemistry	Optional CSF collection ^b
1	1	1	Predose ^a	X	
2	1	1	0.5 to 2 hours		0.5 hours ^b
3	1	1	3.5 to 5 hours	X	4 hours
4	1	3	Predose ^a	X	Predose
5	1	14	Predose ^a	X	Predose
6	1	14	0.5 to 2 hours		0.5 hours
7	1	14	3.5 to 5 hours	X	4 hours
8	1	15	Morning	X	Morning
9	1	16	Morning		

Abbreviations: CSF = cerebrospinal fluid; ECG = electrocardiogram; PK = pharmacokinetic.

^a The predose sample has to be taken before receiving any LY2157299 monohydrate.

^b CSF collection time as close as possible to plasma sample.

Attachment 4. ECOG Performance Status

ECOG Performance Status

Activity Status	Description
0	Fully active, able to carry on all pre-disease performance without restriction
1	Restricted in physically strenuous activity but ambulatory and able to carry out work of a light or sedentary nature, e.g., light house work, office work
2	Ambulatory and capable of all self care but unable to carry out any work activities. Up and about more than 50% of waking hours
3	Capable of only limited self care, confined to bed or chair more than 50% of waking hours
4	Completely disabled. Cannot carry on any self care. Totally confined to bed or chair
5	Dead.

Source: Oken et al. 1982.

Attachment 5. Response Assessment in Neuro-Oncology

Criteria for Determining First Progression Depending On Time from Initial Radiochemotherapy

Twenty percent to 30% of patients develop “pseudoprogression” following radiochemotherapy, especially within the first 3 months following completion of radiotherapy. Given the difficulty of differentiating “pseudoprogression” from true progression in the first 3 months after irradiation, we propose excluding these patients from clinical trials for recurrent disease unless the progression is clearly outside the radiation field (eg, beyond the high dose region or 80% isodose line) or if there is pathologic confirmation of disease progression. Table 2 summarizes these recommendations.

Criteria for Entry into Clinical Trials for Recurrent High-grade Glioma

Currently patients with any worsening of their imaging studies are eligible for entry into clinical trials for recurrent gliomas, even if the change is minimal. It is proposed that patients will be required to have a 25% increase in the sum of the products of perpendicular diameters of the contrast-enhancing lesions on stable or increasing doses of corticosteroids before they are considered to have progressive disease for entry into clinical trials for recurrent/progressive disease. Patients with new contrast-enhancing non-measurable disease may be considered for clinical trials where progression-free survival is the primary endpoint. Clinical deterioration alone would not be sufficient to indicate progressive disease for entry into clinical studies.

A particularly difficult problem involves patients receiving first-line anti-angiogenic agents who develop predominantly non-enhancing disease at progression. This can be difficult to differentiate from treatment effects. If it seems clear that the non-enhancing changes represent tumor progression, these patients would also be eligible for enrollment into clinical trials for recurrent disease, although their tumor will be considered non-measurable. As noted previously, while it would be preferable to have a more objective measure of progressive non-enhancing recurrent disease similar to contrast-enhancing disease, the Response Assessment in Neuro-Oncology (RANO) working group felt that this was not possible at present given the limitations of current technology.

Definition of Radiographic Response

Radiographic response should be determined in comparison to the tumor measurement obtained at pretreatment baseline for determination of response, and the smallest tumor measurement following initiation of therapy for determination of progression. Table 3 outlines the criteria for radiographic changes following therapy. In the event that the radiographic changes are equivocal and it is unclear whether the patient is stable or has developed progressive disease, it is permissible to continue treatment and observe the patients closely, for example at 4 weekly intervals. If subsequent imaging studies demonstrate that progression has occurred, the date of progression should be the scan at which this issue was first raised. All measurable and non-

measurable lesions must be assessed using the same techniques as baseline. Ideally patients should be imaged on the same MRI, or least the same magnet strength, for the duration of the study to reduce difficulties in interpreting changes.

- **Complete Response:** Complete response is defined as complete disappearance of all enhancing measurable and non-measurable disease sustained for at least 4 weeks. In the absence of a confirming scan 4 weeks later, this response will be considered only stable disease. There should be no new lesions. Stable or improved non-enhancing (T2/FLAIR) lesions. Patients must be off corticosteroids and stable or improved clinically.
- **Partial Response:** Greater than or equal to 50% decrease, compared to baseline, in the sum of products of perpendicular diameters of all measurable enhancing lesions sustained for at least 4 weeks. In the absence of a confirming scan 4 weeks later, this response will be considered only stable disease. No progression of non-measurable disease. No new lesions. Stable or improved non-enhancing (T2/FLAIR) lesions on same or lower dose of corticosteroids compared to baseline scan. Patients should be on a corticosteroid dose that should not be greater than the dose at time of baseline scan, and should be stable or improved clinically.
- **Stable Disease:** This occurs if the patients did not qualify for complete response, partial response, or progression (see below). There should be stable non-enhancing (T2/FLAIR) lesions on same or lower dose of corticosteroids compared to baseline scan. In the event that the corticosteroid dose has been increased, the last scan considered to show stable disease will be the scan obtained when the corticosteroid dose was equivalent to the baseline dose. The patient should be stable clinically.
- **Progression:** Progression is defined as $\geq 25\%$ increase in sum of the products of perpendicular diameters of enhancing lesions (over baseline if no decrease) on stable or increasing doses of corticosteroids and/or a significant increase in T2/FLAIR non-enhancing lesion on stable or increasing doses of corticosteroids compared to baseline scan or best response following initiation of therapy, not due to co-morbid events. The appearance of any new lesions. Clear progression of non-measurable lesions. Definite clinical deterioration not attributable to other causes apart from the tumor, or decrease in corticosteroid dose. Failure to return for evaluation due to death or deteriorating condition should also be considered as progression. Increase in corticosteroid dose alone, in the absence of clinical deterioration related to tumor, will not be used as a determinant of progression.

The definition of clinical deterioration is left to the discretion of the treating physician but it is recommended that a decline in the Karnofsky Performance Score (KPS) from 100 or 90 to 70 or less, a decline in KPS of at least 20% from 80 or less, or a decline in KPS from any baseline to 50% or less, for at least 7 days, be considered neurologic deterioration, unless attributable to co-morbid events or changes in corticosteroid dose. Similarly, a decline in the Eastern Cooperative Oncology Group (ECOG) and the World Health Organization (WHO) scores from 0 or 1 to 2, or 2 to 3 would be considered neurologic deterioration.

Patients with non-measurable enhancing disease whose lesion has significantly increased in size and becomes measurable (minimal bidirectional diameter of ≥ 10 mm, and visible on 2 axial slices which are preferably at most 5 mm apart with 0 mm skip) will be considered to have progressed. The transition from a non-measurable lesion to a measurable lesion resulting in progression can theoretically occur with relatively small increases in tumor size (eg, a 9 x 9 mm lesion [non-measurable] increasing to 10 x 11 mm [measurable]). Ideally, the change should be significant (>5 mm increase in maximal diameter or $\geq 25\%$ increase in sum of the products of perpendicular diameters of enhancing lesions). In general, if there is doubt about whether the lesion has progressed, continued treatment and close follow-up evaluation will help clarify whether there is true progression.

If there is uncertainty regarding whether there is progression, the patient may continue on treatment and remain under close observation, for example at 4 weekly intervals. If subsequent evaluations suggest that the patient is in fact progressing, the date of progression should be the time point at which this issue was first raised.

Multifocal Tumors

For multifocal lesions, progressive disease is defined as 25% or greater increase in the sum of products of perpendicular diameters of all measurable lesions compared to the smallest tumor measurements following initiation of therapy (Table 3). Partial response is defined as equal to 50% or greater decrease compared to baseline in the sum of products of perpendicular diameters of all measurable lesions sustained for at least 4 weeks with stable or decreasing corticosteroid doses.

Role of Volumetric and Functional Imaging Assessment

Given the limitations of 2-dimensional (2D) tumor measurements, there is significant interest in volumetric anatomical assessment. The use of volumetric assessment would allow more accurate determination of the contrast-enhancing and non-enhancing volumes, and overcome the limitations of 2D measurements of lesions surrounding a surgical cavity. (Sorensen et al. 2001; Henson et al. 2008; Sorensen et al. 2008). However, the RANO working group and colleagues in neuroradiology did not believe that there is sufficient standardization and availability to recommend adoption of volumetric assessment of tumor volume at present. Nonetheless this is an important area of research. Eventually, as volumetric imaging becomes more standardized and widely available, and as data validating this approach emerges, it may be possible to incorporate volumetric measurements in the response assessment of high-grade gliomas.

There is also emerging data suggesting that advanced MRI techniques such as perfusion imaging (dynamic susceptibility MRI), permeability imaging (dynamic contrast enhanced MRI), diffusion imaging, magnetic resonance spectroscopy, and (18)F-fluorothymidine and amino acid positron emission tomography may predict tumor response or allow the differentiation of non-enhancing tumor from other causes of increased FLAIR signal. These techniques will require rigorous clinical validation studies before they can be incorporated into response criteria used in clinical trials in high-grade gliomas.

Other Methods of Determining Efficacy

There is growing data suggesting that other endpoints such as neuro-cognitive function, quality of life and corticosteroid use may be used to measure clinical benefit. At present, these endpoints are not sufficiently validated to be incorporated into the current response criteria but could be added in the future as further data emerges.

Table 1: Criteria for Determining First Progression Depending On Time from Initial Radiochemotherapy

I. Definition of Progressive Disease Less Than 12 Weeks from Completion of Radiochemotherapy

- a) Progression can only be defined using diagnostic imaging if there is new enhancement outside of the radiation field (beyond the high dose region or 80% isodose line).
or
- b) If there is unequivocal evidence of viable tumor on histopathologic sampling (eg, solid" tumor areas (ie, >70% tumor cell nuclei in areas), high or progressive increase in MIB-1 proliferation index compared to prior biopsy, or evidence for histologic progression or increased anaplasia in tumor.

Note: Given the difficulty of differentiating true progression from "pseudoprogression", clinical decline alone, in the absence of radiographic or histologic confirmation of progression, will not be sufficient for definition of progressive disease in the first 12 weeks following completion of XRT/TMZ.

II. Definition of Progressive Disease at and Beyond 12 Weeks of Radiochemotherapy Completion

- a) New contrast-enhancing lesion outside of radiation field on decreasing, stable or increasing doses of corticosteroids.
- b) Increase by 25% or greater in the sum of the products of perpendicular diameters between the first post-radiotherapy scan, or a subsequent scan with smaller tumor size, and the scan at 12 weeks or later on stable or increasing doses of corticosteroids.
- c) Clinical deterioration not attributable to concurrent medication or comorbid conditions is sufficient to declare progression on current treatment, but not for entry on a clinical trial for recurrence.
- d) For patients receiving anti-angiogenic therapy, significant increase in T2/FLAIR non-enhancing lesion may also be considered progressive disease. The increased T2/FLAIR must have occurred with the patient on stable or increasing doses of corticosteroids compared to baseline scan or best response following initiation of therapy, and not due to co-morbid events (eg, effects of RTX, demyelination, ischemic injury, infection, seizures, post-operative changes, or other treatment effects).

Table 2: Criteria for Response Assessment Incorporating MRI and Clinical Factors

All measurable and non-measurable lesions must be assessed using the same techniques as baseline.

Complete Response:

- a) Complete disappearance of all enhancing measurable and non-measurable disease sustained for at least 4 weeks.
- b) No new lesions.
- c) Stable or improved non-enhancing (T2/FLAIR) lesions
- a) Patients must be on no corticosteroids.
- b) Stable or improved clinically.

Note:

- 1) Patients with non-measurable disease only cannot have a complete response. The best response possible is stable disease.

Partial Response:

- a) Greater than or equal to 50% decrease compared to baseline in the sum of products of perpendicular diameters of all measurable enhancing lesions sustained for at least 4 weeks.
- b) No progression of non-measurable disease.
- c) No new lesions.
- d) Stable or improved non-enhancing (T2/FLAIR) lesions on same or lower dose of corticosteroids compared to baseline scan.
- a) The corticosteroid dose at the time of the scan evaluation should be no greater than the dose at time of baseline scan.
- b) Stable or improved clinically.

Note:

- g) Patients with non-measurable disease only cannot have a partial response. The best response possible is stable disease.

Stable Disease:

- a) Does not qualify for complete response, partial response, or progression.

- b) Stable non-enhancing (T2/FLAIR) lesions on same or lower dose of corticosteroids compared to baseline scan. In the event that the corticosteroid dose has been increased, the last scan considered to show stable disease will be the scan obtained when the corticosteroid dose was equivalent to the baseline dose.
 - a) Stable clinically.

Progression:

- a) $\geq 25\%$ increase in sum of the products of perpendicular diameters of enhancing lesions compared to the smallest tumor measurement obtained either at baseline (if no decrease) or best response, on stable or increasing doses of corticosteroids and/or
- b) Significant increase in T2/FLAIR non-enhancing lesion on stable or increasing doses of corticosteroids compared to baseline scan or best response following initiation of therapy, not due to co-morbid events (eg, RTX, demyelination, ischemic injury, infection, seizures, post-operative changes, or other treatment effects).
- c) Any new lesion
- d) Clear clinical deterioration not attributable to other causes apart from the tumor (eg, seizures, medication side effects, complications of therapy, cerebrovascular events, infection, etc.) or changes in corticosteroid dose.
- e) Failure to return for evaluation due to death or deteriorating condition
- f) Clear progression of non-measurable disease.

Table 3: Summary of the RANO Response Criteria

	CR	PR	SD	PD
T1-Gd +	None	$\geq 50\% \downarrow$	$< 50\% \downarrow -$ $< 25\% \uparrow$	$\geq 25\% \uparrow^*$
T2/FLAIR	Stable or \downarrow	Stable or \downarrow	Stable or \downarrow	\uparrow^*
New Lesion	None	None	None	Present*
Corticosteroids	None	Stable or \downarrow	Stable or \downarrow	NA
Clinical Status	Stable or \uparrow	Stable or \uparrow	Stable or \uparrow	\downarrow^*
Requirement for response	all	all	all	Any*

CR = complete response; PR = partial response; SD = stable disease; PD = progressive disease

\downarrow = decrease

\uparrow = increase

* Progression occurs when any of the criteria with * is present.

NA: Increase in corticosteroids alone will not be taken into account in determining progression in the absence of clinical deterioration.

Reference:

